2.4.2. Study Visits and Periods

2.4.2.1. Screening/Baseline Visit (All Treatment Pathways)

Subjects treated with placebo in their parent study will have a Screening/Baseline visit followed by initiation of AR101 treatment in ARC008, which should occur on the same day as or within 10 days after the Screening/Baseline visit.

Subjects treated with AR101 in their parent study will have a Screening/Baseline visit followed by initiation of AR101 treatment in ARC008, which will occur on the same day as or within 3 days after the Exit visit or Early Discontinuation visit of the subject's parent study, unless specified otherwise in the parent study protocol.

2.4.2.2. Initial Escalation Period (Treatment Pathways 3 and 5)

All Initial Escalation Period doses will be administered by study site personnel under direct observation in the clinic.

Treatment Pathway 3

Eligible subjects will initiate AR101 at a dose of 0.5 mg of AR101 and then increase the dose incrementally at 20- to 30-minute intervals over the course of a single day to a maximum dose of 6 mg.

Subjects who do not tolerate \geq 3 mg dose on Day 1 will discontinue dosing and complete the End of Treatment visit.

Subjects who tolerate \geq 3 mg dose on Day 1 will undergo confirmatory dosing of a single 3 mg dose on the following day, Day 2. Subjects who tolerate this confirmatory dose will enter the Up-Dosing Period. Subjects who do not tolerate this confirmatory dose will discontinue dosing and complete the End of Treatment visit.

Treatment Pathway 5

Eligible subjects will begin initial dose escalation on Day 1 with a stepwise dose escalation of AR101 (up to 4 single doses of 0.5, 1, 1.5, and 3 mg) administered at 20- to 30-minute intervals as tolerated. Subjects who tolerate the 3 mg dose on Day 1 will return on Day 2 for a single 1 mg dose. Subjects who tolerate the 1 mg dose with no more than mild allergy symptoms that are not dose-limiting will begin the Up-Dosing Period. Subjects who do not tolerate any dose on Day 1 or Day 2 will discontinue dosing and complete the End of Treatment visit.

2.4.2.3. Up-Dosing Period (Treatment Pathways 2, 3, and 5)

The Up-Dosing Period is designed to allow stepwise increases in AR101 dose over 2-week intervals to build up tolerance to the allergen while minimizing AEs. The first dose at each new dose level will be administered in the clinic. Subsequent doses will be dispensed to the subject or parent/caregiver and administered at home.

To escalate to the next dose, a subject must be tolerating the current dose. Some subjects may require de-escalation, and once the lower dose is tolerated they may again attempt increasing the dose.

Treatment Pathway 2

Subjects who did not complete their AR101 up-dosing regimen in an eligible parent study will have a Screening/Baseline visit and continue up-dosing in ARC008, proceeding through the applicable study periods until the End of Treatment visit.

Subjects who enter ARC008 soon after completing the ARC004 Early Discontinuation visit will have a Screening/Baseline visit in ARC008 and then enter a Repeat Up-Dosing Period, starting with a daily dose of AR101 at 80, 120, or 160 mg/day at the discretion of the investigator. The dose will be increased every 2 weeks until the maximum daily dose

of 300 mg is reached. Subjects who tolerate the 300 mg/day dose for 2 weeks will receive 300 mg QD for 24 weeks in the Initial Maintenance Period. ARC004 subjects who tolerated the non-daily regimen in ARC004 but who subsequently do not tolerate the non-daily regimen after entering ARC008 Treatment Pathway 1 may switch to Treatment Pathway 2 and start the Repeat Up-Dosing Period at investigator discretion.

Treatment Pathway 3

Subjects in Treatment Pathway 3 will receive AR101 starting at a dose of 3 mg QD and escalate every 2 weeks to a maximum of 300 mg QD, according to the Up-Dosing Schedule. Those subjects who reach the target dose of 300 mg QD of AR101 will take this dose for 2 additional weeks as part of the Up-Dosing Period. Subjects who do not tolerate the 300 mg QD dose of AR101 for 2 weeks within 52 weeks (ie, must reach 300 mg dose by 50 weeks) after starting the Up-Dosing Period will discontinue dosing and complete the End of Treatment visit. Once a subject tolerates the 300 mg dose for 2 weeks in the Up-Dosing Period, the subject will then enter the Initial Maintenance Period and receive the 300 mg dose for 24 weeks.

Treatment Pathway 5

Subjects will receive AR101 starting at the 1 mg/day dose and dose escalation will occur every 2 weeks until the maximum daily dose of 300 mg is reached. Subjects who tolerate the 300 mg/day dose for 2 weeks within 40 weeks after start of up-dosing will begin the Initial Maintenance Period. Subjects who do not tolerate the 300 mg/day dose for 2 weeks within 40 weeks after start of up-dosing will discontinue dosing and complete the End of Treatment visit.

2.4.2.4. Initial Maintenance Period (Pathways 2, 3, and 5)

Subjects in Treatment Pathways 2, 3, and 5 who reach the target dose of 300 mg daily of AR101 and tolerate the dose for 2 additional weeks will return for an in-clinic visit to mark the End of Up-Dosing in this study. The following day, subjects will enter the Initial Maintenance Period and continue dosing with AR101 at 300 mg QD. Dosing on study visit days will take place in the clinic under direct observation.

Subjects in Treatment Pathway 2 who completed the Up-Dosing/Repeat Up-Dosing Period or who tolerated AR101 300 mg QD for 2 weeks in ARC004 will enter the Initial Maintenance Period after the ARC008 Screening/Baseline visit. Subjects who did not complete their AR101 maintenance regimen in an eligible parent study (except study ARC005) will have a Screening/Baseline visit and begin the Initial Maintenance Period in ARC008.

Subjects in Treatment Pathways 2 and 3 will return for in-clinic visits at approximately Weeks 8 and 16 of the Initial Maintenance Period before returning at Week 24 to complete this Period and enter Extended Maintenance.

Subjects in Treatment Pathway 5 will continue initial maintenance (with clinic visits every 4 weeks) for an overall total of approximately 12 months of treatment (including initial dose escalation, up-dosing, and maintenance treatment). The duration of initial maintenance treatment may vary from a minimum of 12 weeks to a maximum of 24 weeks depending on the duration of up-dosing (24-40 weeks). Subjects in Treatment Pathway 5 will have an open-label food challenge (OLFC) at the end of initial maintenance (ie, after an overall total of approximately 12 months of treatment).

2.4.2.5. Extended Maintenance Period (All Treatment Pathways)

The last treatment period for all treatment pathways is the Extended Maintenance Period. Subjects who completed initial maintenance in the parent AR101 study (Treatment Pathways 1 and 4) will enter the Extended Maintenance Period after the Screening/Baseline visit, and the other subjects (Treatment Pathways 2, 3, and 5) will enter this period after completing the Initial Maintenance Period in this study, after completing both the Repeat Up-Dosing and Initial Maintenance Periods in their parent study, or after receiving AR101 300 mg QD for at least 24 weeks in their parent study.

During the Extended Maintenance Period, subjects will continue their current dosing regimen (300 mg QD, every other day [QOD], twice weekly [BIW], once weekly [QW], or every other week [QOW]), and study visits will occur approximately every 3 months. Subjects in Treatment Pathways 1, 2, and 3 who enter this period will have the option to participate in an OLFC to assess level of desensitization to peanut protein after 12 months in the Extended Maintenance Period and yearly thereafter. For subjects in Treatment Pathways 4 and 5, the OLFC after the first 12 months of extended maintenance treatment is required and then optional yearly thereafter.

2.4.2.6. End of Treatment Visit (All Treatment Pathways)

After protocol amendment 6.0 is approved at the study site:

- Subjects in the United States (US) from prior studies ARC007 and ARC011 who have access to commercially available product will have the End of Treatment visit at their next scheduled study site (not remote) visit.
- Subjects in the US from prior studies ARC002 or ARC004 who have access to commercially available product may have the End of Treatment visit at their next scheduled study site (not remote) visit if so directed by the study sponsor when necessary for operational considerations.

- Subjects from prior study ARC005 will return to the study site for the End of Treatment visit when they complete at least approximately 3 years total of AR101 treatment including study ARC005 and AR101 is commercially available in their country, or discontinue early.
- All other subjects will return to the study site for the End of Treatment visit when they complete at least approximately 5 years total of AR101 treatment including all prior studies and AR101 is commercially available in their country, or discontinue early.

A DBPCFC will be performed at the End of Treatment visit; subjects who discontinue AR101 treatment early for safety reasons will not have the DBPCFC. All subjects will have telephone follow-up at least 14 days after the last dose of AR101 or last food challenge, whichever is last.

2.4.2.7. Follow-Up Observation Period (All Treatment Pathways)

The End of Treatment visit will be followed by a 12-month observation period. During observation, management of peanut allergy will be guided by the subject's physician. Observation assessments will be conducted by telephone at 3, 6, and 9 months to enquire about the following:

- Current treatment plan (eg, commercially available product, complete peanut avoidance, use of food equivalents for peanut oral immunotherapy, other investigational immunotherapy, other)
- Events of systemic allergic reactions, eosinophilic esophagitis (EoE), accidental/non-accidental exposures to food allergens and their outcomes, use of epinephrine, hospitalizations (all causes), emergency department visits (all causes), and serious adverse events (SAEs)

2.4.2.8. Study Exit Visit (All Treatment Pathways)

The Study Exit visit will be conducted approximately 12 months after the last dose of AR101. An optional DBPCFC may be performed.

2.5. DETERMINATION OF SAMPLE SIZE

The potential number of subjects who may be enrolled in this study is approximately 950. The sample size will be determined by the number of eligible subjects from each of the prior AR101 studies who participate in this study.

2.6. TREATMENT ASSIGNMENT

ARC008 is an open-label study. Subjects will receive AR101 in 1 of 5 treatment pathways in ARC008 as described in Section 2.4.

2.7. ADMINISTRATION OF STUDY TREATMENT

AR101 is characterized peanut allergen in the form of peanut flour, formulated with a bulking agent (maize starch, microcrystalline cellulose, and other excipients to prevent clumping) and a flow agent in premeasured graduated doses. The capsules used in the Initial Escalation Period and Up-Dosing Period of this study currently include the following strengths: 0.5, 1, 10, 20, and 100 mg each of peanut protein.

AR101 capsules will be provided in prepackaged dosing kits. For the escalation periods, each individual kit will contain 21 daily doses at a given dose level, enough to supply 2 weeks of dosing plus a 7-day overage to accommodate potential visit scheduling issues.

For Initial and Extended Maintenance Period dosing, a 300 mg AR101 dose will be provided in sealed, foil-laminate (1 sachet/day). Sachets will be provided in kits containing 35 individual doses.

All doses scheduled to be administered on clinic visit days will be taken at the clinic. Subjects should withhold their daily home AR101 dose on in-clinic dosing days. At each clinic visit in the Up-Dosing, Initial Maintenance, and Extended Maintenance Periods, the subject or parent/caregiver will receive a kit of capsules or sachets to be taken at home according to the current dose level. For Treatment Pathways 4 and 5 only, the parent/caregiver will be instructed to record the capsules/sachets taken at home in a diary log.

3. ENDPOINTS

3.1. SAFETY ENDPOINTS

The primary safety endpoints are as follows:

- Frequency of AEs
- Frequency of premature discontinuation of AR101 dosing due to AEs
- Frequency of premature discontinuation of dosing due to chronic/recurrent gastrointestinal (GI) AEs
- Frequency of AEs that lead to a change in treatment regimen
- Frequency of AEs that lead to early withdrawal
- Frequency of anaphylaxis
- Frequency of use of epinephrine as a rescue medication
- Frequency of accidental/non-accidental ingestion of peanut and other allergenic foods
- Frequency of AEs following accidental/non-accidental exposure to peanut and other allergenic foods
- Frequency of EoE

The secondary safety endpoints are as follows:

- Change in peak expiratory flow (PEF)
- Change in Childhood Asthma Control Test (C-ACT) and Asthma Control Test (ACT) score
- Change in Total Nasal Symptom Score (TNSS)

3.2. EFFICACY ENDPOINTS

The secondary efficacy endpoints are as follows:

• Proportion of subjects tolerating each challenge dose in the OLFC and the DBPCFC

- The maximum tolerated challenge dose at each food challenge
- Change in tolerated dose of peanut protein
- Maximum severity of symptoms in each food challenge
- Frequency of use of epinephrine as a rescue medication during the food challenges
- Changes in food allergy QoL scores as measured by Food Allergy Quality of Life Questionnaires (FAQLQ), and the Food Allergy Independent Measure (FAIM) questionnaire
- Change in Food Allergy Quality of Life Parental Burden (FAQL-PB) questionnaire score

3.3. EXPLORATORY ENDPOINTS

The exploratory endpoints are as follows:

- Change in peanut-specific (ps) and peanut component-specific serum immunoglobulin G subclass 4 (IgG4)
- Change in total, peanut-specific, and peanut component-specific serum immunoglobulin E (IgE)
- Change in peanut skin prick test (SPT) mean wheal diameter
- Change in Test for Respiratory and Asthma Control in Kids (TRACK) and Eczema Area and Severity Index (EASI) scores

4. ANALYSIS POPULATION

The following analysis population will be defined for this study:

Safety Population: The Safety Population will consist of all subjects who receive AR101 during ARC008. The Safety Population will be used for all analyses.

5. **PROTOCOL DEVIATIONS**

Any change, divergence, or departure from the study design or procedures constitutes a protocol deviation. All protocol deviations will be reported on a specific case report form (CRF) as follows:

- Inclusion Criteria
- Exclusion Criteria
- Received Incorrect Study Treatment
- Informed Consent Form (ICF)
- SAE Not Reported
- Visit Out Of Window
- Missed Study Visit
- Procedure Not Per Protocol
- Prohibited Concomitant Medication
- Lab Sample Missed
- Study Drug Compliance
- Other, Specify

These protocol deviations will be reviewed prior to database lock and their categorization as major or minor will be determined prior to database lock. All protocol deviations, both major and non-major, will be listed and included in the study report.

6. GENERAL ASPECTS FOR STATISTICAL ANALYSIS

6.1. STATISTICAL NOTATION AND METHODOLOGY

Unless otherwise stated, the term "descriptive statistics" refers to the number of subjects (n), mean, median, standard deviation, minimum, and maximum for continuous variables and frequencies and percentages for categorical variables.

Unless specified otherwise, the denominator for percentages for categorical data will be based on the number of subjects or observations with non-missing data appropriate for summary purposes. The denominator for percentages for incidence data (such as AEs) will be based on the number of subjects in the analysis population "at risk". Select ordinal data may be summarized using both descriptive statistics and counts and percentages of subjects in each category, as appropriate.

Minimum and maximum values will be presented at the precision of the original value, means and medians will be rounded to 1 decimal place greater than the precision of the original value, standard deviations and standard errors will be rounded to 2 decimal places greater than the precision of the original value. Percentages will be rounded to 1 decimal place. Percentages that round down to 0 or up to 100% will be displayed as "<0.1%" and ">99.9%", respectively. Other statistics (e.g., confidence intervals [CIs]) will be presented using the same general rules outlined above or assessed for the most appropriate presentation based on the underlying data.

Unless otherwise noted, values reported as greater than or less than some quantifiable limit (e.g., "< 1.0") will be summarized with the sign suppressed in summary tables and figures, using the numeric value reported. Data will display on subject listings to include the sign.

In general, summary tables will be presented by combining subjects from each of the treatment pathways into a single treatment group (AR101).

All relevant data collected in the database and any derived data will be included in data listings and unless otherwise noted sorted by treatment pathway, subject ID, test/measurement, and visit and time point as appropriate.

All statistical methods will be based on the International Conference on Harmonisation (ICH)-E9 Guidance for Industry "Statistical Principles for Clinical Trials".

A review of the database will be conducted before database lock. Any decision to amend the planned statistical analysis will be documented in an amendment to the SAP prior to database lock and details will be included in the clinical study report (CSR).

If the assumptions underlying the formal statistical methods proposed are not met during the analysis of the final data, an alternative, more appropriate, statistical method will be

used and any changes documented in the statistical methods section of the CSR, including the rationale for use.

Additional exploratory analyses of the data will be conducted as deemed appropriate. These analyses will be fully documented and clearly identified as post-hoc and exploratory.

6.2. STRATA AND COVARIATES

There are no planned applications of covariate adjustments or stratification; all statistical results are descriptive in nature.

6.3. SUBGROUP ANALYSES

The overall summary of treatment-emergent adverse events (TEAEs) and treatmentemergent serious adverse events (TESAEs) (Section 9.1) and the summary of rescue medications (Section 9.12) will be repeated for the following subgroups:

- Treatment Pathways 1-3
- Treatment Pathways 4-5
- Daily dosing regimen
- Non-daily dosing regimen

Daily and non-daily dosing regimen subgroups are based on the initial regimen assigned in ARC008.

The overall summary of treatment-emergent AEs of interest (AEIs) and treatmentemergent serious AEIs will also be summarized separately for Treatment Pathways 1-3 and 4-5.

Immunoglobulin values will also be summarized separately for Treatment Pathways 1-3, 4, and 5.

6.4. MULTIPLE COMPARISONS AND MULTIPLICITY

No adjustments will be made for multiple comparisons. Results are descriptive in nature and there will be no formal comparisons made.

6.5. SIGNIFICANCE LEVEL

No formal statistical analysis will be performed. This study is exploratory in nature; descriptive statistics will be tabulated and reviewed to evaluate all study endpoints.

7. DATA HANDLING METHODS

7.1. VISIT WINDOWS

All data other than those described below will be listed, summarized, and analyzed according to the nominal visit time points or study period.

7.1.1. Subjects Tolerating Each Challenge Dose and the Maximum Tolerated Dose at Each OLFC

In the summary and listings of subjects tolerating each OLFC dose and the maximum tolerated dose (MTD) at each food challenge (Section 10.1), visits will be reassigned to a study visit based on the actual days relative to the start of Extended Maintenance using the visit windows identified in Table 1 below. As described in Section 2.4, subjects in Treatment Pathway 5 will have an OLFC at the End of Initial Maintenance (ie, after an overall total of approximately 12 months of treatment). Subjects in Treatment Pathways 1, 2, and 3 will have the option to participate in an OLFC after 12 months in the Extended Maintenance Period and yearly thereafter. For subjects in Treatment Pathways 4 and 5, the OLFC after the first 12 months of extended maintenance treatment is required and then optional yearly thereafter. Visit windows are therefore defined to capture all possible OLFCs for each treatment pathway.

For Treatment Pathways 1 and 4, the start of Extended Maintenance is defined as the date and time of first in-clinic or at home dose of treatment in ARC008. For Treatment Pathways 2, 3, and 5, the start of an Extended Maintenance is defined as the first visit labeled as an Extended Maintenance visit.

Treatment		Months Since Start of Extended Maintenance	
Pathway	Visit	Target Month	Window Interval
5	End of Initial Maintenance	0	< 6
1-4	Extended Maintenance: Month 12	12	< 18
5	Extended Maintenance: Month 12	12	[6,18)
All (1-5)	Extended Maintenance: Month 24	24	[18, 30)
All (1-5)	Extended Maintenance: Month 36	36	[30, 42)
All (1-5)	Extended Maintenance: Month 48	48	[42, 54)
All (1-5)	Extended Maintenance: Month 60	60	\geq 54

Table 1Visit Windows for Analysis of Subjects Tolerating Each Challenge Doseand the MTD at Each Food Challenge

If more than one value is mapped to the same visit, the value collected closest to the target month will be considered for summarization. If two values collected on different days are mapped to the same scheduled visit and are equidistant from the target month, the earlier of the values will be considered.

7.1.2. Peanut-Specific and Peanut Component-Specific IgE and IgG4

In the summaries of peanut-specific and peanut component-specific IgE and IgG4 (Section 11.1), End of Up-Dosing, End of Initial Maintenance, and Extended Maintenance visits will be reassigned to a study visit based on the actual days relative to the start of Extended Maintenance using the visit windows identified in Table 2 below. According to schedules of events in the appendices of the protocol, subjects in Treatment Pathways 2 and 3 will have scheduled immunology blood sample collection at End of Up-Dosing and subjects in Treatment Pathways 2, 3, and 5 will have a scheduled collection at the End of Initial Maintenance. Subjects from all treatment pathways will also have scheduled blood sample collection after the first 12 months of extended maintenance treatment and yearly thereafter as well as at End of Treatment and Study Exit. Visit windows are therefore defined to capture all scheduled blood sample collection for each treatment pathway. Nominal visits will be used in the summary of End of Treatment and Study Exit visits.

For Treatment Pathways 1 and 4, the start of Extended Maintenance is defined as the date and time of first in-clinic or at home dose of treatment in ARC008. For Treatment Pathways 2, 3, and 5, the start of an Extended Maintenance is defined as the first visit labeled as an Extended Maintenance visit.

Treatment		Months Since Start of Extended Maintenance	
Pathway	Visit	Target Month	Window Interval
2, 3	End of Up-Dosing	-6	< 0
2, 3	End of Initial Maintenance	0	[0, 6)
5	End of Initial Maintenance	0	< 6
1, 4	Extended Maintenance: Month 12	12	[0, 18)
2, 3, 5	Extended Maintenance: Month 12	12	[6, 18)
All (1-5)	Extended Maintenance: Month 24	24	[18, 30)
All (1-5)	Extended Maintenance: Month 36	36	[30, 42)
All (1-5)	Extended Maintenance: Month 48	48	[42, 54)
All (1-5)	Extended Maintenance: Month 60	60	≥ 54

Table 2 Visit Windows for Analysis of Immunoglobulin Results

If more than one value is mapped to the same visit, the value collected closest to the target month will be considered for summarization. If two values collected on different days are mapped to the same scheduled visit and are equidistant from the target month, the earlier of the values will be considered. Nominal visits will be presented in the data listings of peanut-specific and peanut component-specific IgE and IgG4 results.

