3.2.8 Study Exit Visit (All Treatment Pathways)

The Study Exit visit will be conducted approximately 12 months after the last dose of AR101. An optional DBPCFC may be performed.

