3.7 Study Discontinuation

Each subject will continue in the study until 1 or more of the following events occurs:

- The risk/benefit profile for the subject to continue in the study is no longer favorable in the opinion of the investigator.
- The investigator withdraws the subject from the study.
- The subject withdraws consent.
- The sponsor discontinues development of AR101 in the relevant participating country.
- Subject completes the End of Treatment visit and the 1-year follow-up observation period.

After one of these events occurs, the subject will return to the clinic for an End of Treatment or Study Exit visit, as appropriate.

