7.7. DATA ADJUDICATION

As the study ended much earlier than originally anticipated some of the locked or frozen data had to be adjudicated by the Nestle Health Science study team. All outcomes of this adjudication are documented in the Site Closure Plan, Adjudication Charter and in Appendix A.

Additional data issues and analysis issues identified during the analysis and how they were handled are captured in separate tracking documents.

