8. DEMOGRAPHIC, OTHER BASELINE CHARACTERISTICS

8.1. SUBJECT DISPOSITION AND WITHDRAWALS

Subject disposition and completion status will be summarized for all screened subjects. The number and percentage of subjects who were screened, were screen failures, were included in each analysis population, were in each treatment pathway, were assigned to daily/non-daily dosing regimens, entered each study period, completed all dosing as defined in the protocol, completed the study per protocol, and completed the safety follow-up per protocol will also be summarized.

Reason for early treatment discontinuation, early study discontinuation, and premature discontinuation from follow-up, including due to COVID-19 related reasons, will be summarized as well as whether subjects required follow-up due to chronic/recurrent GI symptoms.

The dates of last study visit, last contact, and study completion/early discontinuation will be listed as well as reason for early treatment discontinuation, reason for early study discontinuation, and reason for premature discontinuation from follow-up. Follow-up status for subjects who required follow-up due to recurrent GI symptoms will also be included in the subject data listings.

Inclusion and exclusion eligibility will be listed separately.

8.2. **PROTOCOL DEVIATIONS**

Major protocol deviations (identified by sponsor review before database lock) will be summarized for the Safety Population. All protocol deviations, as defined in Section 5, will be listed by treatment pathway and subject ID.

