11. ANALYSIS OF EXPLORATORY ENDPOINTS

11.1. PEANUT-SPECIFIC AND PEANUT COMPONENT-SPECIFIC IGE AND IGG4

Blood samples to measure ps-IgE, ps-IgG₄ levels, and total IgE levels will be collected at the timepoints as indicated in the schedules of events in the appendices of the protocol.

Ps-IgE/IgG₄ ratio will be calculated, listed by subject, and summarized by visit and treatment group (AR101). Results outside the limits of quantification will be displayed as less than the lower limit of quantification (LLOQ), or greater than the upper limit of quantification (ULOQ), as appropriate. These values will be summarized as either the LLOQ or the ULOQ. If the ps-IgE or ps-IgG₄ is outside of the limits of quantification, the ps-IgE/IgG₄ ratio will be calculated using the LLOQ or ULOQ as appropriate.

Summary statistics, including geometric means and geometric standard deviations, will be presented by time point and years of total AR101 exposure including parent studies and overall separately for Treatment Pathways 1-3, 4, and 5.

Summaries of change from baseline to Study Exit visit for total IgE, ps-IgE, ps-IgG₄, ps-IgE/IgG₄ ratio, peanut-specific IgE and IgG4 components (Ara h 1, Ara h 2, Ara h 3, Ara h 8, Ara h 9) and the corresponding IgE/IgG4 ratio of each component will be presented using change calculated on the log₁₀ scale.

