11.2. SKIN PRICK TEST

SPTs will be conducted at the visits indicated in the schedules of events in the appendices of the protocol. Results from the SPT will be listed by treatment pathway, subject ID, and visit, including test date and time, and measurements (in mm) of the following: peanut wheal (long axis), peanut wheal (short axis), saline wheal (long axis), saline wheal (short axis), histamine wheal (long axis), and histamine wheal (short axis).

A derived mean wheal diameter score will be calculated as the average of the long and short axis from the peanut wheal minus the average of the long and short axis from the saline wheal. Summary statistics for the derived SPT mean wheal diameter will be presented at each visit, for change from baseline to End of Treatment, and for change from baseline to Study Exit visit by years of total AR101 exposure including parent studies and overall.

11.3. TEST FOR RESPIRATORY AND ASTHMA CONTROL IN KIDS (TRACK) AND ECZEMA AREA AND SEVERITY INDEX (EASI)

TRACK and EASI scores are measured as indicated in the schedules of events in the appendices of the protocol.

TRACK

In Treatment Pathways 4 and 5, asthma control in subjects aged 1 to < 5 years with preexisting asthma will be assessed using TRACK scores and by the incidence of asthma rescue medication use. Subjects who turn age 5 years during the study or who are aged \geq 5 years at enrollment in Treatment Pathways 4 and 5 will be administered the C-ACT questionnaire instead of the TRACK questionnaire.

The TRACK questionnaire will be administered at the visits indicated in the schedules of events in the appendices of the protocol. The parent/caregiver is to complete the TRACK, a 5-item standardized questionnaire used to evaluate respiratory and asthma control in children aged < 5 years with symptoms consistent with asthma (Zeiger, 2011). Each item is scored on a 5-point scale from 0 (4 or more times a week) to 20 (not at all). Higher scores indicate better respiratory and asthma control.

EASI

For subjects with pre-existing eczema or atopic dermatitis in Treatment Pathways 4 and 5, the severity of clinical signs of eczema or atopic dermatitis will be assessed using the EASI scoring system. Higher scores indicate greater severity of eczema or atopic dermatitis.

A listing of the results from the TRACK and EASI questionnaires will be provided, sorted by treatment pathway, subject ID, and visit.

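### Study Exit immunoglobulin and skin prick results are summarized by visit label, so the change-to-Study-Exit tables can pool different intervals since the last study dose

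*SAP*

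**What the plan says.** SAP 7.1 sets a default: "All data other than those described below will be listed, summarized, and analyzed according to the nominal visit time points or study period". Sections 7.1.2 (immunoglobulins) and 7.1.3 (skin prick test) are exceptions to it. They map End of Up-Dosing, End of Initial Maintenance and Extended Maintenance results to visits by actual time from the start of Extended Maintenance, using Tables 2 and 3. Each section then puts the last two visits back on their labels: "Nominal visits will be used in the summary of End of Treatment and Study Exit visits".

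Protocol 3.2.8 fixes when Study Exit should happen: "The Study Exit visit will be conducted approximately 12 months after the last dose of AR101". The visit descriptions in Protocol Section 7 also give 12 months, with no tolerance in the body text.

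Protocol 3.7 lists the events that end participation, including withdrawal of consent, withdrawal by the investigator and the sponsor ceasing development in a country. It continues: "After one of these events occurs, the subject will return to the clinic for an End of Treatment or Study Exit visit, as appropriate". SAP 8.1 expects some subjects to leave in follow-up. It summarizes "Reason for early treatment discontinuation, early study discontinuation, and premature discontinuation from follow-up".

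Two analyses use the visit. SAP 11.1 plans "Summaries of change from baseline to Study Exit visit for total IgE" and the other immunoglobulin measures, on the log10 scale. SAP 11.2 summarizes skin prick wheal diameter "for change from baseline to Study Exit visit by years of total AR101 exposure including parent studies and overall".

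**The concern.** Study Exit has meaning in these tables only as a time point about a year after dosing stops. Protocol 3.4.1 gives assessment of sustained effect as the reason for the observation period, and an exploratory objective covers immunologic parameters after the last dose. If a sample taken a few months after the last dose carries the same label as one taken at 12 months, the row no longer describes a 12-month follow-up, and nothing in the table shows this.

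Few other planned summaries cover this ground. SAP 10.1 summarizes the DBPCFC at End of Treatment, and SAP 10.3 only lists the FAQLQ and FAIM scores. Immunoglobulins and skin prick results are the efficacy or exploratory outcomes for which I find an explicit Study Exit summary.

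**Working it through.** The documents give no figure to reproduce, so the check is mainly a comparison of sections.

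1. **Which visits have a time rule.** In Tables 2 and 3 the Extended Maintenance rows for Months 24 to 48 are bounded on both sides, for example 18 to under 30 months for Month 24. End of Treatment and Study Exit have no window. For End of Treatment this matters less, because that visit is tied to the end of dosing itself. Study Exit is defined by time elapsed since dosing, so a missing bound matters more.

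2. **Who can have an early Study Exit visit.**
   - *Stopping AR101 early:* this does not by itself produce one. Protocol 4.4 sends the subject to End of Treatment, and Protocol 3.2.7 follows that visit with 12 months of observation.
   - *Leaving the study during follow-up:* this can. The subject has already had End of Treatment, so of the two visits named in Protocol 3.7, Study Exit is the one left. That is my reading of a sentence that leaves the choice open, but SAP 1.3 supports it by naming Study Exit and Early Discontinuation assessments together.
   - *Closure:* this can, if it cuts a subject's follow-up short.

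3. **Whether a later rule separates the intervals.** SAP Table 4 ends the follow-up period at the Study Exit date, or at study completion if there is none, with no minimum length. The split by years of total AR101 exposure concerns time on drug, not time since the last dose. The SAP text supplied has no sensitivity analysis for Study Exit timing.

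4. **What pooling does to the interval (assumed inputs only).** Suppose a share f of Study Exit visits falls at m months and the rest at 12. The mean interval is 12 − f × (12 − m).

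| f | m (months) | Mean interval (months) |
|---|---|---|
| 10% | 9 | 12 − 0.10 × 3 = 11.7 |
| 10% | 6 | 12 − 0.10 × 6 = 11.4 |
| 30% | 3 | 12 − 0.30 × 9 = 9.3 |
| 50% | 3 | 12 − 0.50 × 9 = 7.5 |

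The documents give neither f nor m. The range runs from negligible to material, and it describes the interval only, not the effect on any immunologic result.

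**The case against.** The strongest reply is that no early Study Exit visit is documented. SAP 7.7 says "As the study ended much earlier than originally anticipated some of the locked or frozen data had to be adjudicated", and a reader might infer that closure shortened follow-up. The sentence does not say so: it explains why data were adjudicated. Against a planned duration of about 10 years, earlier End of Treatment visits with a full observation year would fit equally well. This stands. The documents show that early visits are possible, not that they were common.

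A reader might also infer that pooling early exits makes the effect look more durable. That does not follow either. Protocol 3.2.7 lists commercial product, food equivalents for oral immunotherapy and other investigational immunotherapy among the possible treatment plans during observation. A subject seen at 12 months may be on peanut immunotherapy while one seen at 3 months is not. The interval is time since the last study dose, not time off treatment. A percentage dilution of post-treatment change would not describe the planned tables, because they report change from a baseline taken before the first ARC008 dose (SAP 7.4).

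Some safeguards exist. Out-of-window visits are a recorded deviation category, visit dates are listed, and reasons for leaving follow-up are tabulated. These let a reader trace individual cases but do not correct the summary rows. Protocol Appendix 6, SAP Appendix A, the Site Closure Plan and the Adjudication Charter are not in the text reviewed and may hold a visit tolerance or an adjudication rule. A scheduling tolerance alone would not change the SAP's assignment by label.

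**Conclusion.** The point holds as a limit on interpretation. As written, the Study Exit rows for immunoglobulins and skin prick tests can combine different intervals since the last study dose, so they may not represent the intended 12-month follow-up. This rests on the explicit label rule and on reading Protocol 3.7 as allowing Study Exit before month 12 for a subject who leaves in follow-up. The frequency of early visits and the direction and size of any bias cannot be determined from the documents.

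The stakes are modest. These are exploratory endpoints summarized descriptively, and no hypothesis test, power calculation or primary safety conclusion depends on them. The change is still worth making, because it is cheap and the tables otherwise do not show what interval they describe.

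**What to change.** For SAP 7.1.2 and 7.1.3, derive months since last study dose as (Study Exit assessment date − date of last study AR101 dose) ÷ (365.25/12), the conversion in SAP 7.4. In each Study Exit immunoglobulin and skin prick table:

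- report the median and range of that interval;
- present visits within a stated window around 12 months separately from those outside it. The window could be the protocol's own visit tolerance if one exists, or for example 10 to 14 months. At 30.4375 days per month, that is 10 × 30.4375 ≈ 304 to 14 × 30.4375 ≈ 426 days.

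The window does not resolve the mixing of treatments during follow-up, so a table note should say that the interval runs from the last study dose.

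SAP 1.1 dates Version 2 after database lock and restricts its updates to Appendix A. If added now, the analysis should be labelled post hoc, which SAP 6.1 allows for additional exploratory work. The cost is one derived variable from dates already held, an extra row per table, and fewer subjects in the 12-month row.
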